1.0 Objectives

1.1 Study Objectives

Aim: To determine the effect on food and energy intake of varying the proportion of lower-energy-dense vegetables and fruits in meals served over five days to preschool children.

Hypotheses:

1. When low-energy-dense vegetables and fruits are added to children's meals over five days (Addition condition):
 - a. Daily energy intake will increase compared to the Baseline condition
 - b. Daily vegetable and fruit intake will increase compared to the Baseline condition
 - c. Daily food and beverage intake will increase compared to the Baseline condition
 - d. Daily food energy density will decrease compared to the Baseline condition
2. When low-energy-dense vegetables and fruits are substituted for foods higher in energy density in children's meals over five days (Substitution condition):
 - a. Daily energy intake will
 - i. decrease compared to the Baseline condition
 - ii. decrease compared to the Addition condition
 - b. Daily vegetable and fruit intake will
 - i. increase compared to the Baseline condition
 - ii. increase compared to the Addition condition
 - c. Daily food and beverage intake will
 - i. not differ significantly from the Baseline condition
 - ii. decrease compared to the Addition condition
 - d. Daily food energy density will
 - i. decrease compared to the Baseline condition
 - ii. decrease compared to the Addition condition
3. Across all three conditions of different proportions of low-energy-dense vegetables and fruits, daily intakes of vegetables, fruit, and energy will begin to converge over the five-day period

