1.2 Primary Study Endpoints

1. Differences in food and beverage intake by energy [Time Frame: Day 1-5 in Weeks 1, 2, and 3]
Energy intake in kcal
2. Differences in food and beverage intake by weight [Time Frame: Day 1-5 in Weeks 1, 2, and 3]
Weight consumed in grams (g)

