6.0 Study Design and Procedures

6.1 Study Design

This study will have a within-subjects crossover design with repeated measures across five days of meals and three experimental conditions. The investigators will vary the proportions of low-energy-dense vegetables and fruits served at meals by either addition or substitution. In the three experimental conditions, the same foods will be served - only the amounts and proportions of foods will be varied. In the Baseline condition, typical proportions of age-appropriate foods will be served. In the Addition condition, the portion sizes of low-energy-dense vegetables and fruits will be increased, and in the Substitution condition, the portions of low-energy-dense vegetables and fruits will be increased by replacing an equivalent weight of foods higher in energy density. The order of the conditions across the three experimental periods, as well as the order of the five menus within each five-day period, will be counterbalanced by classroom. The three five-day experimental periods will be separated by a two-week washout period. All menus in all conditions will meet the minimum requirements of the United State Department of Agriculture (USDA) Child and Adult Care Food Program (CACFP) [3].

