6.2 Study Procedures

1. Over five consecutive days, enrolled children will be served breakfast, lunch, dinner, and snacks of foods commonly served in the childcare center following their regular meal and snack schedules - menus were developed from the menus at the childcare centers to be as similar as possible to the foods that children are regularly served. Milk or water will be served as beverages. Meals will be served at tables of three to six children and one adult, which is a standard practice at the childcare centers. The adults at the table will be instructed not to discuss the food or to encourage the children to eat. There will be three conditions, with changes only in the proportion of lower-energy-dense vegetables and fruits at the meals. Each participant will be served an individual pre-weighed meal. All food and beverage items will be weighed with a food scale before and after meals and snacks to within 1 gram in order to determine the amount consumed. Participants will be told they can eat as much or as little of the foods as they would like. Trained observers (research personnel) will document food and beverage spillage and any comments made about the food. The children will be provided with an evening snack pre-packaged for consumption at home. Any leftover food from the evening snack will be returned to the childcare center the following day to be weighed.
2. In the event of extenuating circumstances (e.g. unexpected childcare center closure, inclement weather) the researchers may decide to pack out a meal, or meals, which can be consumed outside of the childcare center. Participants will be notified in advance if this should occur. Any leftover food from a packed meal, or meals, will be returned to the childcare center the following day to be weighed. Applicable instructions for serving or reheating will be provided.
3. Parents will be asked not to serve any additional food or beverages to their child apart from those provided by the study and water. If the participant deviates from the procedure and consumes extra food, the estimated food and beverage consumption will be requested.

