7.0 Statistical Plan

7.1 Sample size determination

The sample size for the study was based on the statistical power to detect differences in energy intake between the Baseline and Substitution conditions across study days. The sample size was estimated from a linear mixed model and an approximation technique [4] using exemplary data sets based on our previous five-day studies in preschool children [1,2]. We assumed that the minimum clinically significant difference in energy intake across days was 50 kcal, which is about 5% of daily intake for a typical preschool child. To detect this change over time with a Type 1 error rate of 5% and power of 90%, it was determined that 48 participants would be required. To allow for withdrawals and non-compliance to the protocol, 55 to 60 children will be enrolled.

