7.2 Statistical methods

The study hypotheses will be assessed using linear mixed models with repeated measures. Differences in mean outcomes will be tested across the three experimental conditions of the proportion of vegetables and fruits served in meals, as well as across the five days of intake.

Hypotheses 1 and 2 test whether variations in the proportion of low- and high-energy-dense foods influence the mean daily outcomes of energy intake, food and beverage intake, and energy density. To test these hypotheses, the fixed factors in the models will be condition, study week, study day, menu, childcare center, classroom, and sex. Interactions between these factors will be tested and removed from the model if not significant and participants will be treated as a random effect. The Tukey-Kramer method will be used to adjust for multiple pairwise comparisons between means. The energy content of parentally reported non-study food consumption will be estimated by research staff. Daily energy intake will be analyzed both with and without the non-study items.

Hypothesis 3, concerning whether daily energy intake in the three conditions converges over each five-day period, tests whether regulation of energy intake occurs over time in response to variations in the proportion of low- and high-energy-dense foods served. To test this hypothesis, a random coefficients model will be used. The trajectories of intake over time will be allowed to vary randomly across subjects; thus, they will be modeled separately for each child. Time (study day) will be treated as a continuous covariate in the model and polynomial factors of time (linear and quadratic coefficients) will be tested as both fixed and random effects to determine the shape of the intake trajectory. The intercept of the trajectory will reflect the magnitude of daily intake at Day 1

and the linear coefficient will represent the rate of change in intake (slope) across time after Day 1. The quadratic coefficient, if significant, will represent the rate of acceleration or deceleration in intake (curvature) across time after Day 1.

It has been predetermined that children who have incomplete intake measures on ≥ 3 days in all 3 conditions will be excluded from analysis. It has also been predetermined that children who eat $>95\%$ of the food weight served on at least 1 day will be classified as “plate cleaners”, and their influence on the results will be tested.

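### Hypothesis 2c(i), on the primary endpoint of intake by weight, predicts no significant difference, but the plan has only a difference test, so a non-significant result would count as support

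*Combined protocol and SAP*

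**What the plan says.** Section 1.1 lists numbered hypotheses. Under Substitution, 2a concerns energy, 2b vegetables and fruit, 2c food and beverage intake, and 2d energy density. Part 2c(i) predicts that intake will "not differ significantly from the Baseline condition". Since energy and energy density have their own hypotheses, 2c must be intake by weight. That is the second primary endpoint in section 1.2: "Differences in food and beverage intake by weight", measured in grams.

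On analysis, section 7.2 states: "The study hypotheses will be assessed using linear mixed models with repeated measures". It continues: "Differences in mean outcomes will be tested across the three experimental conditions". For pairs of conditions, "The Tukey-Kramer method will be used to adjust for multiple pairwise comparisons between means". The significance level is p < 0.05. The text names food and beverage intake among the outcomes of these models, so 2c is covered by them. Neither document section gives an equivalence test, a margin, a confidence interval criterion or a smallest important difference in grams.

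Section 7.1 bases the sample size on the "statistical power to detect differences in energy intake between the Baseline and Substitution conditions". Weight is not mentioned there.

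**The concern.** A test for a difference can show that two means differ. When it fails to reject, it does not show that they are alike. Because 2c(i) is worded in terms of significance and the only criterion is p < 0.05, the prediction is met whenever the adjusted p value is 0.05 or more. The incentives then run backwards: losing children, noisier weighing or a stricter multiplicity adjustment all make support for the hypothesis more likely.

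The prediction has substance. Substitution works by "replacing an equivalent weight of foods higher in energy density" (section 6.1), so the weight served matches Baseline by design, and 2c(i) asks whether the weight eaten does too. As the plan stands, the report could say that a primary endpoint was unchanged when the data cannot exclude a change that matters. The chance of that false conclusion is neither stated nor limited in advance.

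**Working it through.** **The plan's own figure.** Section 7.1 gives 48 children to detect 50 kcal (about 5% of daily intake, hence about 1000 kcal per day) with 5% type 1 error and 90% power. It states no SD, so 48 cannot be reproduced independently. Working backwards from a paired comparison of means, two-sided and unadjusted, the within-child SD of the difference would be 50 × √48 / (1.960 + 1.2816) = 106.9 kcal. This is implied by 48 and does not confirm it.

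**Precision implied for energy.** The Tukey critical value for three means with large degrees of freedom is 2.344. There are two readings of the power calculation:

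- Planned without Tukey: SE = 50 / (1.960 + 1.2816) = 15.42 kcal, or 1.54% of 1000 kcal.
- Planned with Tukey: SE = 50 / (2.344 + 1.2816) = 13.79 kcal, or 1.38%.

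**Assumptions for weight.** Weight has the same relative SE as energy; a 5% difference in weight is worth detecting; the power calculation was for a mean contrast; tests are two-sided. None of these is stated in the documents for weight. Weight also includes drinks ("Milk or water will be served as beverages", section 6.2), so its precision may differ either way.

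**Risk under the current wording, and performance of an equivalence rule.** The chance that a true 5% difference is non-significant under Tukey is Φ(2.344 − 5/SE%). The equivalence rule uses two one-sided 5% tests with a ±5% margin; its power at a true difference of zero is 2Φ(5/SE% − 1.645) − 1. For another sample size n, SE is multiplied by √(48/n). In each cell the first figure is for planning without Tukey, the second for planning with it.

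| Scenario | True 5% difference called non-significant | Equivalence power at zero difference |
|---|---|---|
| n = 48 | 18.5% / 10.0% | 89% / 95% |
| n = 40 | 26.9% / 16.7% | 81% / 90% |
| n = 55 | 13.0% / 6.2% | 93% / 97% |
| n = 60 | 10.0% / 4.4% | 95% / 98% |
| n = 48, SE 1.5 times larger | 57.2% / 47.1% | 39% / 56% |
| n = 48, SE 1.5 times smaller | 0.6% / 0.1% | above 99% |

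For example, with n = 48 and planning without Tukey: 5/1.542 = 3.242, and Φ(2.344 − 3.242) = 18.5%.

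For a true 2.5% difference at n = 48, non-significance occurs 77% or 70% of the time. Under the equivalence rule, a claim of similarity when the true difference is 5% occurs at most 5% of the time in every row.

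**The case against.** The strongest reply is that the decision rule is inferred. Section 1.1 states an expectation, and nothing in section 7.2 says that p ≥ 0.05 will be reported as proof of no change. The mixed model yields an estimate and interval anyway, and a careful report would give them. This is fair as far as it goes. But section 7.2 says the hypotheses are assessed by these models, and it offers no other criterion by which 2c(i) could succeed or fail.

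Second, the reach is narrow. Hypotheses 1c and 2c(ii), also on weight, are directional and suit the planned test. Only one of the three weight contrasts is affected. That stands.

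Third, the percentages are not evidence from this trial. They borrow precision from energy, and section 7.1 speaks of change over time, so the back-calculated SE may not apply even to energy. Across the scenarios the risk runs from about 0.1% to 57%. Enrolment is 55 to 60, so analysing only 40 would mean losing 15 to 20 children (27% to 33%). All of this is right, and it limits the numbers to illustration. The 5% ceiling under the equivalence rule is likewise a property of setting the margin at 5%.

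Finally, with high precision a difference could be both Tukey-significant and inside the margin. This needs SE below 5 / (2.344 + 1.645) = 1.25%, and at n = 60 with planning under Tukey (SE 1.23%) the window is narrow: 2.89% to 2.97%. The two statements are compatible, since a difference can be real and smaller than the margin.

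**Conclusion.** The concern holds. The plan applies the wrong inference rule to one numbered hypothesis on a primary endpoint. That conclusion rests on the wording of 2c(i) and on the absence of any margin or interval criterion, together with two small inferences: that 2c means weight, and that p ≥ 0.05 is what fulfils it. It needs no figure from the sample size section.

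The size is uncertain. Under energy-like precision the false conclusion at a true 5% difference is a modest risk at 48 children and smaller at full enrolment. It becomes roughly an even chance if weight is measured 1.5 times less precisely. This should be corrected before analysis, but it does not threaten the energy comparisons, on which the sample size is based, or the two directional weight hypotheses.

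**What to change.** In section 1.1, reword 2c(i) so that non-significance is not confirmation, for example: daily intake by weight will be similar to Baseline, judged by the criterion in section 7.2.

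In section 7.2, add the following:

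- Report the Substitution minus Baseline difference in daily weight, in grams, with its confidence interval.
- Claim similar intake only if the 90% confidence interval (two one-sided tests at 5%, outside the Tukey-Kramer family) lies wholly within a margin in grams that the investigators justify and fix before analysis. Plus or minus 5% of Baseline is one candidate, by analogy with the energy threshold in section 7.1, but the documents do not set it for weight.
- Treat a non-significant difference that fails the criterion as inconclusive. If a difference is significant and also inside the margin, report both facts.
- If no margin can be justified, give the estimate and interval and make no claim of equality.

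The cost is a few sentences and one extra interval, with no new data or children. The margin for weight needs its own justification, and the result may be inconclusive where the present wording would have said no difference, particularly if weight proves more variable than energy.

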1.2 Primary Study Endpoints

1. Differences in food and beverage intake by energy [Time Frame: Day 1-5 in Weeks 1, 2, and 3]
Energy intake in kcal
2. Differences in food and beverage intake by weight [Time Frame: Day 1-5 in Weeks 1, 2, and 3]
Weight consumed in grams (g)

1.3 Secondary Study Endpoints

1. Differences in food and beverage intake by energy density [Time Frame: Day 1-5 in Weeks 1, 2, and 3]
Energy density in kcal/g

2.0 Background

2.1 Scientific Background and Gaps

It has been proposed that preschool children are in a formative stage during which the ability to regulate energy intake is being replaced by eating in response to environmental food cues. In recent studies, we have found that increases in both food portion size (g) and energy density (kcal/g) have been robust in promoting excess energy intake in preschool children [1,2]. These results challenge the proposition that preschool children show self-regulatory behavior by altering their energy intake when it is perturbed by variations in the available foods.

At present no controlled studies have been conducted over a sufficient duration to determine whether preschool children adjust for energy imbalances stemming from changes in the proportions of foods lower and higher in energy density served at meals.

2.2 Previous Data

N/A

2.3 Study Rationale

This study will provide a better understanding of the regulation of energy intake in preschool children over multiple days by determining how intake is affected by changing the proportions of foods lower and higher in energy density that are served at meals.

3.0 Inclusion and Exclusion Criteria

3.1 Inclusion Criteria

1. Children who are enrolled in a participating childcare center
2. Children who are between the ages of 3 and 5 years old at the time of enrollment
3. Parents of children enrolled in the study who are 18 years or older
4. Teacher in a classroom with enrolled children who are 18 years or older

3.2 Exclusion Criteria

1. Allergy to any of the foods served
2. Children whose diets exclude any of the foods served (e.g. vegan, vegetarian, gluten-free)
3. Children who are not planning to be present for all three study weeks (e.g. planned vacation during a study week)

3.3 Early Withdrawal of Subjects

3.3.1 Criteria for removal from study

Subjects will be removed from the study if they miss three or more days in one study week or two meals per day for three or more days in one study week.

Subjects will also be removed from the study if they repeatedly fail to follow study protocol.

All participation is voluntary and a child can refuse a session and parents may withdraw from the study at any time.

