3.3.2 Follow-up for withdrawn subjects

N/A

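### One poorly attended week removes a child from the whole crossover, so later conditions go unrecorded, although the section 7.2 analysis rule would keep that child

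*Combined protocol and SAP*

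**What the plan says.** Four parts of the protocol bear on this.

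- **Removal (3.3.1).** "Subjects will be removed from the study if they miss three or more days in one study week". A second trigger has the same effect: absence from two of a day's meals on at least three days of a week. Either trigger is met by a single week, and the consequence is removal from the study, not from that week.
- **After removal (3.3.2).** The only entry under this heading is N/A.
- **Design (6.1).** "This study will have a within-subjects crossover design with repeated measures across five days of meals and three experimental conditions". Condition order is counterbalanced by classroom, so any condition can fall after the poorly attended week.
- **Analysis (7.2).** The models are linear mixed models in which "participants will be treated as a random effect". The exclusion rule is that "children who have incomplete intake measures on ≥ 3 days in all 3 conditions will be excluded from analysis".

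The protocol gives no reason for the removal rule. It does not say whether intake recorded before a removal is analysed.

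**The concern.** The comparison of interest is within child, so a child's later weeks have most of their value when an earlier week is poor: they can still form a complete pair. Section 3.2 already excludes children with planned absences. The attendance rule will therefore mainly catch unplanned ones, such as a short illness, in children who may be back at the center for the next study week. The packed-meal option in 6.2 is for events such as center closure or bad weather, and is not described as cover for one child's absence.

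The conduct rule and the analysis rule treat the same child differently. With one poor week and two good ones, 7.2 would keep the child, but 3.3.1 stops collection at the first poor week. If that is week 1, removal itself leaves all three conditions incomplete, and the child then appears to meet the 7.2 exclusion. The conduct rule has turned an analysable child into an excluded one.

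At stake is avoidable missing data, selected on attendance. Height and weight are scheduled for the 16th visit and the parent questionnaires for the last five study days (6.2), so a child removed in week 1 or 2 has neither under that schedule.

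**Working it through.** **The plan's own figure.** Section 7.1 requires 48 children for 90% power at a 5% type 1 error rate to detect 50 kcal between Baseline and Substitution, and enrols 55 to 60. No standard deviation or covariance is given, so 48 cannot be reproduced. Back-solving the paired formula n = (SD × (1.960 + 1.282) / 50)² at n = 48, two-sided, gives SD = 50 × √48 / 3.2415 = 106.9 kcal for the within-child difference. Sidedness is not stated; one-sided, the value would be 118.4. I use 106.9 only to convert pair counts into power.

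**Assumed failure rate.** The documents give no absence rate. Let p be the probability that a child-week fails an attendance threshold, independently across weeks. The allowance is 1 − 48/55 = 12.7% to 1 − 48/60 = 20.0%. If this rule alone used all of it, p = 1 − (48/55)^(1/3) = 4.4% or p = 1 − (48/60)^(1/3) = 7.2%. The table uses 5% and 7.2% with 60 enrolled (180 child-weeks).

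**What one failing week costs.**

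- Week 1 fails: the full week 2 vs week 3 comparison is lost, plus two comparisons with the partial week 1.
- Week 2 fails: the full week 1 vs week 3 comparison is lost, plus the partial week 2 vs week 3.
- Week 3 fails: no later week exists to lose.

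**Formulas.**

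- Children removed = 60 × [1 − (1−p)³].
- Usable later weeks not collected = 60 × (1−p) × [p + 1 − (1−p)²]. The two terms are a good week 2 after a failed week 1, and a good week 3 after any earlier failure.
- Complete pairs per contrast if children stay = 60 × (1−p)².
- Complete pairs under 3.3.1 = 60 × [(1−p)² + 2(1−p)³] / 3. The week 1–2 pair needs two good weeks. The other two pairs need all three, because any earlier failure stops collection. The average assumes balanced order and that data before removal are used.

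| | p = 5% | p = 7.2% |
|---|---|---|
| Children removed | 8.6 | 12.0 |
| Usable child-weeks not collected | 8.4 (4.7%) | 11.7 (6.5%) |
| Pairs if children stay | 54.2 | 51.7 |
| Pairs under 3.3.1, earlier data used | 52.3 | 49.2 |
| Pairs if all the child's data are dropped, 60(1−p)³ | 51.4 | 48.0 |
| Power, same order | 93.1%, 92.3%, 91.9% | 92.0%, 90.7%, 90.0% |

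The cost of the rule is 0.8 to 1.3 points of power if earlier data are used, and 1.2 to 2.0 if they are dropped. With earlier data used, the standard error rises by √(54.15/52.34) = 1.017 to √(51.71/49.24) = 1.025, about 2%.

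**Sensitivity.** With 55 enrolled and p = 4.4%, pairs are 50.2 against 48.7 (power 91.2% against 90.4%). With 55 enrolled and p = 10%, beyond the allowance, they are 44.6 against 41.6 (87.8% against 85.5%).

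**The poor week itself.** These counts give it no credit. If f is the share of the difference variance at week level (assumed), a 2-day week paired with a 5-day week carries 1 / [f + 1.75(1−f)] of the information in a full pair, where 1.75 = (1/2 + 1/5) / (1/5 + 1/5). That is 57% at f = 0 and 84% at f = 0.75.

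**The case against.** The strongest reply is that the loss is small and already budgeted. Section 7.1 enrols extra children for withdrawal and non-compliance, and at 60 enrolled both rates in the table leave at least 48 pairs even under the rule. That stands, and a reader who infers that the sample size fails goes further than the documents allow.

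The assumptions also favor the concern. At 7.2% the whole allowance goes to this one rule, leaving nothing for parental withdrawal or repeated protocol failure. If absence clusters within children, those removed early would be likelier to fail later weeks too, and fewer weeks would be recovered. Both criticisms stand; the 7.2% column is an upper value within the plan's allowance.

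Three stronger readings are tempting and not supported:

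- That the rule has no benefit. The protocol states none, but participation totals 39 hours (6.3) with daily weighed meals and evening forms, so burden or cost may lie behind it.
- That a week-1 failure costs three full comparisons. It costs one full comparison; the other two involve the partial week, which the absence had already damaged.
- That counterbalancing is undermined. Losses do build up by week (57.0, 54.2 and 51.4 adequate weeks at p = 5%), but order is counterbalanced by classroom and study week is a fixed factor in the model. Nothing in the documents shows a condition-specific loss or a bias.

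Finally, 3.3.1 governs conduct and 7.2 governs analysis, and missed days are not the same thing as incomplete measures. The two rules can formally coexist. That does not explain why collection should stop for a child whom the analysis would keep.

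**Conclusion.** The point holds as one of avoidable missing data and of two rules that do not fit together. The mechanism follows directly from 3.3.1 and 3.3.2 and needs no assumption: a failure in week 1 or 2 means later conditions are never recorded. About a third of removals would come from week 3 (0.05 × 0.95² / (1 − 0.95³) = 32% at p = 5%), and these lose no later week.

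The size is modest: about 8 to 12 usable child-weeks of 180, about two complete pairs per contrast, and about 1 to 2 points of power. These figures rest on an assumed, independent failure rate of 5% to 7.2%, balanced order, and a standard deviation back-solved from 48. The change is worth making because it is cheap and improves completeness, not because the trial would otherwise be underpowered.

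**What to change.** Amend 3.3.1 so that failing either attendance threshold in one study week does not by itself remove the child. Specifically:

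- Keep serving and measuring willing children on every day they attend, both in the rest of that week and in the later study weeks.
- State in 7.2 that all validly measured days enter the mixed model, including days before any withdrawal.
- Let the 7.2 rule decide analysis inclusion, and confirm that its all-three-conditions wording is intended. If any one condition was meant, 3.3.1 and 7.2 would agree with each other, but that is not what is written.
- Leave voluntary withdrawal and removal for repeated failure to follow the protocol unchanged.

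The cost is a short edit to 3.3.1 and a sentence or two in 7.2, plus meals and measurement for a few more children in weeks already being run in their classrooms.
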